 - Patients with controlled Type 1 diabetes mellitus on a stable insulin regimen may be eligible for this study after discussion with and approval by the Medical Monitor.
- Prior allogeneic stem cell or solid organ transplantation
- History of idiopathic pulmonary fibrosis, organizing pneumonia (e.g., bronchiolitis obliterans), drug-induced pneumonitis, idiopathic pneumonitis, or evidence of active pneumonitis on screening chest computed tomography (CT) scan
 - History of radiation pneumonitis in the radiation field (fibrosis) is permitted.
- Serum albumin < 2.5 g/dL
- Positive test for HIV
- Active hepatitis B (defined as having a positive hepatitis B surface antigen [HBsAg] test at screening)
 - Patients with past or resolved hepatitis B (HBV) infection (defined as having a negative HBsAg test and a positive anti-hepatitis B core antigen [anti-HBc] antibody test) are eligible. HBV DNA must be obtained in these patients prior to the first dose of study treatment.
- Active hepatitis C
 - Patients positive for hepatitis C virus (HCV) antibody are eligible only if polymerase chain reaction assay is negative for HCV RNA.
- Active tuberculosis

- Severe infections within 28 days prior to the first dose of study treatment, including but not limited to hospitalization for complications of infection, bacteremia, or severe pneumonia
- Signs or symptoms of infection within 14 days prior to the first dose of study treatment
- Treatment with therapeutic oral or IV antibiotics within 14 days prior to the first dose of study treatment
 - Patients receiving prophylactic antibiotics (e.g., to prevent a urinary tract infection or chronic obstructive pulmonary disease exacerbation) are eligible.
- Significant cardiovascular disease, such as New York Heart Association cardiac disease (Class II or greater), myocardial infarction within the previous 3 months, unstable arrhythmias, or unstable angina
- Major surgical procedure other than for diagnosis within 28 days prior to the first dose of study treatment, or anticipation of need for a major surgical procedure during the course of the study
- Administration of a live/attenuated vaccine within 28 days prior to the first dose of study treatment, within 5 months following the administration of the last dose of study drug, or anticipation that such a live/attenuated vaccine will be required during the study

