Patients with a history of autoimmune-related hypothyroidism on a stable dose of thyroid-replacement hormone may be eligible for this study after discussion with and approval by the Medical Monitor.

Patients with controlled Type 1 diabetes mellitus on a stable insulin regimen may be eligible for this study after discussion with and approval by the Medical Monitor.

- Prior allogeneic stem cell or solid organ transplantation
- History of idiopathic pulmonary fibrosis, organizing pneumonia (e.g., bronchiolitis obliterans), drug-induced pneumonitis, idiopathic pneumonitis, or evidence of active pneumonitis on screening chest CT scan

History of radiation pneumonitis in the radiation field (fibrosis) is permitted.

- Serum albumin <2.5 g/dL
- Positive test for HIV
- Active hepatitis B (defined as having a positive hepatitis B surface antigen [HBsAg] test at screening)

Patients with past or resolved hepatitis B (HBV) infection (defined as having a negative HBsAg test and a positive anti-hepatitis B core antigen [anti-HBc] antibody test) are eligible. HBV DNA must be obtained in these patients prior to the first dose of study treatment.

- Active hepatitis C

Patients positive for hepatitis C virus (HCV) antibody are eligible only if polymerase chain reaction assay is negative for HCV RNA.

- Active tuberculosis
- Severe infections within 28 days prior to the first dose of study treatment, including but not limited to hospitalization for complications of infection, bacteremia, or severe pneumonia
- Signs or symptoms of infection within 14 days prior to the first dose of study treatment
- Treatment with therapeutic oral or IV antibiotics within 14 days prior to the first dose of study treatment

Patients receiving prophylactic antibiotics (e.g., to prevent a urinary tract infection or chronic obstructive pulmonary disease exacerbation) are eligible.

- Significant cardiovascular disease, such as New York Heart Association cardiac disease (Class II or greater), myocardial infarction within the previous 3 months, unstable arrhythmias, or unstable angina
- Major surgical procedure other than for diagnosis within 28 days prior to the first dose of study treatment, or anticipation of need for a major surgical procedure during the course of the study

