4.5.1 Informed Consent Forms and Screening Log

Written informed consent for participation in the study must be obtained before performing any study-specific screening tests or evaluations.

Informed Consent Forms for enrolled patients and for patients who are not subsequently enrolled will be maintained at the study site.

All screening evaluations must be completed and reviewed to confirm that patients meet all eligibility criteria before enrollment. The investigator will maintain a screening log to record details of all patients screened and to confirm eligibility or record reasons for screening failure, as applicable.

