4.5.6 Laboratory, Biomarker, and Other Biological Samples

Local laboratory assessments will include the following:

- Hematology (CBC, including RBC count, hemoglobin, hematocrit, WBC count with differential [neutrophils, eosinophils, lymphocytes, monocytes, basophils, and other cells], and platelet count)
- Serum chemistries (glucose, BUN or urea, creatinine, sodium, potassium, magnesium, chloride, bicarbonate, calcium, phosphorus, total bilirubin, ALT, AST, alkaline phosphatase, LDH, total protein, and albumin)
- Coagulation panel (aPTT and INR)
- Serum pregnancy test (for women of childbearing potential, including premenopausal women who have had a tubal ligation)
- Creatinine clearance (calculated using the Cockcroft-Gault formula)
- Urinalysis (specific gravity, pH, glucose, protein, ketones, and blood)
- Thyroid function testing (thyroid-stimulating hormone [TSH], free T3, free T4)
- All patients will have a QuantiFERON blood test done locally prior to inclusion into the study
- HBV serology (HBsAg, antibodies against HBsAg, anti-hepatitis B core antibody [HBc Ab])
 - HBV DNA should be obtained prior to the first dose of study treatment if the patient has positive serology for anti-HBc Ab.
- HCV serology (anti-HCV)
- HIV serology

Central laboratories will coordinate the collection of archival and tumor tissue as well as blood samples for the assessment of atezolizumab pharmacokinetics and biomarkers, ATA assays, and auto-antibody testing. The following assessments will be performed at a central laboratory or at Roche:

- ATA assays
 - Serum samples will be assayed for the presence of ATAs to atezolizumab with use of validated immunoassays.
- PK assay
 - Serum samples will be assayed for atezolizumab concentration with use of a validated immunoassay.
- Biomarker assays in blood
 - Blood samples will be obtained at various timepoints, including at disease progression, for biomarker evaluation (including but not limited to biomarkers that are related to bladder or tumor immune biology) from all eligible patients according to the schedule in [Appendix 4](#) and [Appendix 5](#). Specifically, at disease progression, samples will be processed to obtain EDTA plasma for the determination of changes in blood-based biomarkers. Whole blood samples may be processed to obtain peripheral blood mononuclear cells (PBMCs) and their derivatives (e.g., RNA).

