 - ^k Baseline upper urinary tract imaging with CT urography, intravenous pyelogram, renal ultrasound with retrograde pyelogram, ureteroscopy or MRI urogram. Pelvic CT before TURBT may be considered but is not required. Assessment should be within 28 days prior to starting study treatment. Upper tract imaging using the same modality as was used at baseline should be performed at the 6-month (atezolizumab Cycle 9, Day 1) and 18-month (atezolizumab Cycle 29, Day 1) assessments, and then annually as indicated.
 - ^l Patients with recurrent low-grade papillary disease will be required to undergo resection with TURBT (unless medically contraindicated) and may continue in the study and receive study treatment. Patients with persistent and/or recurrent high-grade NMIBC without progression at 12 weeks may continue in the study, provided there is no evidence of progression to muscle-invasive disease. Patients with persistent and/or recurrent high-grade NMIBC at the 6-month assessment will be discontinued from study therapy. Patients with progression to muscle invasion at any time will be discontinued from study therapy.
 - ^m Includes RBC count, hemoglobin, hematocrit, WBC count with automated differential (neutrophils, lymphocytes, eosinophils, monocytes, basophils, and other cells), and platelet count. A manual differential can be done if clinically indicated.
 - ⁿ Laboratory results to be obtained within 14 days prior to the first dose of atezolizumab treatment.
 - ^o Includes BUN, creatinine, sodium, potassium, magnesium, chloride, bicarbonate, calcium, phosphorus, glucose, total bilirubin, ALT, AST, alkaline phosphatase, LDH, total protein, and albumin.

Appendix 1

Schedule of Assessments: Cohort 1A (cont.)

- ^p Urinalysis (specific gravity, pH, glucose, protein, ketones, and blood).
- ^q HIV testing to be performed in accordance with national and/or institutional guidelines. HBV DNA must be collected on or before Cycle 1, Day 1 in patients who have negative serology for hepatitis B surface antigen and positive serology for anti-HCV.
- ^r All patients will have a QuantiFERON[®] test done locally prior to inclusion into the study.
- ^s Serum pregnancy test (for women of childbearing potential, including women who have had a tubal ligation) must be performed and documented as negative within 14 days prior to Cycle 1, Day 1, q3w, and at treatment completion/discontinuation.

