- ^l Patients with recurrent low-grade papillary disease will be required to undergo resection with TURBT (unless medically contraindicated) and may continue in the study and receive study treatment. Patients with persistent and/or recurrent high-grade NMIBC without progression at 12 weeks may continue in the study provided there is no evidence of progression to muscle invasive disease. Patients with persistent and/or recurrent high-grade NMIBC at the 6-month assessment will be discontinued from study therapy. Patients with progression to muscle invasion at any time will be discontinued from study therapy.
- ^m Includes RBC count, hemoglobin, hematocrit, WBC count with automated differential (neutrophils, lymphocytes, eosinophils, monocytes, basophils, and other cells), and platelet count. A manual differential can be done if clinically indicated.
- ⁿ Laboratory results to be obtained within 14 days prior to the first dose of atezolizumab treatment.
- ^o Includes BUN, creatinine, sodium, potassium, magnesium, chloride, bicarbonate, calcium, phosphorus, glucose, total bilirubin, ALT, AST, alkaline phosphatase, LDH, total protein, and albumin.
- ^p Urinalysis (specific gravity, pH, glucose, protein, ketones, and blood).
- ^q HIV testing to be performed in accordance with national and/or institutional guidelines. HBV DNA must be collected on or before Cycle 1, Day 1 in patients who have negative serology for hepatitis B surface antigen and positive serology for anti HCV.
- ^r All patients will have a QuantiFERON[®] test done locally prior to inclusion into the study.
- ^s Serum pregnancy test (for women of childbearing potential, including women who have had a tubal ligation) must be performed and documented as negative within 14 days prior to Cycle 1, Day 1 and at treatment completion/discontinuation.
- ^t A sample of tumor tissue is required at study entry. Fresh tissue biopsy is preferred; however, an archival specimen may be submitted in lieu of fresh tissue if a tissue biopsy is contraindicated owing to patient safety or tumor tissue accessibility and the archival specimen was obtained within 2 months of study screening. The specimen may consist of a FFPE tumor tissue block (preferred) or at least 10 unstained, serial sections.

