Pulmonary event, Grade 2	
 • Withhold atezolizumab for up to 12 weeks after event onset.^a • Refer patient to pulmonary and infectious disease specialists and consider bronchoscopy or BAL. • Initiate treatment with 1–2 mg/kg/day oral prednisone or equivalent. • If event resolves to Grade 1 or better, resume atezolizumab.^b • If event does not resolve to Grade 1 or better while withholding atezolizumab, permanently discontinue atezolizumab and contact Medical Monitor.^c • For recurrent events, treat as a Grade 3 or 4 event.
Pulmonary event, Grade 3 or 4	
 • Permanently discontinue atezolizumab and contact Medical Monitor.^c • Bronchoscopy or BAL is recommended. • Initiate treatment with 1–2 mg/kg/day oral prednisone or equivalent. • If event does not improve within 48 hours after initiating corticosteroids, consider adding an immunosuppressive agent. • If event resolves to Grade 1 or better, taper corticosteroids over ≥ 1 month.

BAL = bronchoscopic alveolar lavage.

- ^a Atezolizumab may be withheld for a longer period of time (i.e., > 12 weeks after event onset) to allow for corticosteroids (if initiated) to be reduced to ≤ 10 mg/day oral prednisone or equivalent. The acceptable length of the extended period of time must be agreed upon by the investigator and the Medical Monitor.
- ^b If corticosteroids have been initiated, they must be tapered over ≥ 1 month to ≤ 10 mg/day oral prednisone or equivalent before atezolizumab can be resumed.
- ^c Resumption of atezolizumab may be considered in patients who are deriving benefit and have fully recovered from the *immune-mediated* event. Patients can be re-challenged with atezolizumab only after approval has been documented by both the investigator (or an appropriate delegate) and the Medical Monitor.

Appendix 12

Risks Associated with Atezolizumab and Guidelines for Management of Adverse Events Associated with Atezolizumab (cont.)

HEPATIC EVENTS

Immune-mediated hepatitis has been associated with the administration of atezolizumab. Eligible patients must have adequate liver function, as manifested by measurements of total bilirubin and hepatic transaminases, and liver function will be monitored throughout study treatment. Management guidelines for hepatic events are provided in [Table 2](#).

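### Footnote q in both schedules of assessments ties HBV DNA testing to hepatitis C antibody, whereas the synopsis and Sections 4.1.2 and 4.5.6 tie it to hepatitis B core antibody

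*Combined protocol and SAP*

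**What the plan says.** The condition for HBV DNA testing is stated in five places.

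- **Protocol Synopsis and Section 4.1.2, Exclusion Criteria.** Patients with past or resolved hepatitis B may enter. This state is "defined as having a negative HBsAg test and a positive anti-hepatitis B core antigen [anti-HBc] antibody test". Section 4.1.2 adds: "HBV DNA must be obtained in these patients prior to the first dose of study treatment". The synopsis has the same requirement.
- **Section 4.5.6, laboratory assessments.** "HBV DNA should be obtained prior to the first dose of study treatment if the patient has positive serology for anti-HBc Ab".
- **Appendix 1, footnote q (Cohort 1A).** Collection on or before Cycle 1, Day 1 is mandatory in patients with "negative serology for hepatitis B surface antigen and positive serology for anti-HCV".
- **Appendix 2, footnote q (Cohorts 1B, 2 and 3).** The condition is the same, printed without the hyphen: "negative serology for hepatitis B surface antigen and positive serology for anti HCV".

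Section 4.1.2 deals with HCV antibody separately: "Patients positive for hepatitis C virus (HCV) antibody are eligible only if polymerase chain reaction assay is negative for HCV RNA". Nothing in the body of the protocol links HCV antibody to HBV DNA.

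**The concern.** Section 4.5 sends sites to Appendices 1 and 2 for the assessments to be performed. Neither schedule has a row for HBV DNA. Footnote q, attached to the combined HIV, HBV and HCV serology row, is the only instruction about it there, and it is worded as an obligation. A coordinator working from the schedule would therefore order HBV DNA on the wrong marker.

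What is at stake is a baseline safety test. Appendix 12 states: "Immune-mediated hepatitis has been associated with the administration of atezolizumab". It also asks that viral hepatitis be considered when liver tests rise, and it directs corticosteroids for persistent Grade 2 and for Grade 3 or 4 hepatic events. Section 3.1.4 counts certain Grade 3 or higher hepatic toxicities as dose-limiting if judged related to atezolizumab or to the combination. In a patient with resolved hepatitis B, a missing baseline HBV DNA makes it harder to attribute a later liver event. Omitting the test would also depart from Section 4.1.2 even though the site had followed its schedule.

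**Working it through.** The plan gives no figure to reproduce, so the check compares the texts and then counts.

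**Step 1: which side is in error.** Three statements use anti-HBc (synopsis, 4.1.2, 4.5.6) and two use anti-HCV (footnote q, twice). The footnotes keep the HBsAg-negative half of the resolved-hepatitis-B definition but replace the second marker with one that belongs to a different virus and has its own follow-up test in 4.1.2. That points to a drafting slip in the footnotes. A text-extraction fault is unlikely, because the wording occurs in two separate footnotes with different punctuation.

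**Step 2: where the rules differ.** HBsAg-positive patients are excluded, so only HBsAg-negative patients matter.

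| anti-HBc | anti-HCV | Body text (synopsis, 4.1.2, 4.5.6) | Footnote q | Consequence of using the footnote alone |
|---|---|---|---|---|
| + | − | test | no test | required test missed |
| − | + | no test | test | unnecessary test |
| + | + | test | test | none |
| − | − | no test | no test | none |

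The rules differ in 2 of 4 patterns. One of these is a possible missed test.

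**Step 3: how many patients.** Maximum planned enrollment in Section 3.1.1 is 12 (Cohort 1A) + 18 (Cohort 1B) + 10 (Cohort 1 expansion) + 10 (Cohort 2) + 10 (Cohort 3) + 10 (Cohorts 2 and 3 expansion) = 70. The documents do not say how common anti-HBc positivity is. Let *p* be the assumed share of enrolled patients who are anti-HBc positive and anti-HCV negative. The number exposed to the omission is 70 × *p*:

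- *p* = 0.01: 70 × 0.01 = 0.7
- *p* = 0.05: 70 × 0.05 = 3.5
- *p* = 0.10: 70 × 0.10 = 7.0

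For each assumed *p* this is a ceiling, because a site that also applies 4.1.2 or 4.5.6 would order the test. It does not bound the true number, since *p* itself is unknown.

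**The case against.** The strongest reply is that this is an editorial slip with several safeguards around it.

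- The correct rule appears three times, including in the eligibility criteria. Section 4.5.1 says: "All screening evaluations must be completed and reviewed to confirm that patients meet all eligibility criteria before enrollment". Both schedules also carry a screening row for review of eligibility criteria, so even a schedule-driven site is pointed to 4.1.2.
- Neither schedule names anti-HBc. A site learns that it must be drawn from Section 4.5.6, where the correct HBV DNA rule sits directly under the HBV serology list.
- Footnote q does not say that only the patients it names are to be tested. A site could satisfy both rules by testing everyone named by either.
- The documents do not say that atezolizumab reactivates hepatitis B. Liver tests are done on Day 1 of every cycle, AST and ALT are capped at entry, and hepatitis is immediately reportable.
- The prevalence scenarios have no support in the documents.

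Most of this stands as a limit on the consequence. A miss requires a site to use the footnote without the body text, and later liver monitoring reduces the harm. It does not remove the error. Testing under both rules requires a site to notice that the footnote is incomplete, and on-treatment liver tests cannot supply a pre-dose HBV DNA result. The scenarios show scale only; the conclusion does not depend on them.

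**Conclusion.** The inconsistency is real, it is in current protocol text, and between them the two footnotes cover every cohort. Followed alone, footnote q omits the pre-dose HBV DNA test in the very patient for whom Section 4.1.2 requires it, and adds an unneeded test in the opposite pattern. The conflict itself rests on the wording alone and needs no assumption. The patient counts rest on the assumed prevalence and on sites relying solely on the footnote.

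The consequence is confined to a possible missed baseline safety test. No HBV DNA level decides entry, and the result enters no endpoint, sample size or analysis. It should be corrected, but it does not threaten the trial's conclusions.

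**What to change.** In footnote q of Appendix 1 and of Appendix 2, replace the hepatitis C antibody marker with anti-HBc. Leave the synopsis and Sections 4.1.2 and 4.5.6 as they are; all five statements then agree on the marker.

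The cost is one word in each of two footnotes, with no change to intended procedures, sample size or analysis. If patients have already been screened, check that those positive for anti-HBc had HBV DNA obtained before their first dose.
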